9.4 EVALUATION AT 12 MONTHS OF DISCHARGE

Re-evaluate the following aspects by phone

- Mortality
- Functionality data (Barthel index, Lawton index , PASE Scale).
- Usual medication.
- Residency at the moment.
- Frailty with the FRAIL scale. Datos de fragilidad con la escala FRAIL.
- Data of quality of life with the scale EuroQolfive-dimensional (EQ-5D)
- Number of hospitalization and ER, indicate the cause (diagnosis)
- Burden of the caregiver with the economics questionnaires.
- Economics evaluation., Index 3

9.5 END OF THE STUDY EVALUATION

- The study will finish at 12 months after patient's discharge with a lastphone call .
- We should make an effort to write all the data during the study, at follow up and the final evaluation..

A follow-up and investigator's tasks schedule was performed during the study. See table 2.

Table 2 Schedule of the investigation

Intervention phase	Eligibility&recruitment	Initial Visit	Discharge	3 month Follow-up	12 month Follow-up
Informed consent	X				
Eligibility CI and CE	X	X			
Medical history		X			
Usual treatment		X	X	X	X
Comprehensive Geriatric Assessment		X			
Cognitive and depression (MMSE,GDS,CAM)		X			
Comorbidities - Charlson I.		X			
Functional Status (Barthel I, Lawton I, PASE, SPBB)		X SPBB	X Barthel	X	X
Sociodemographic data		X			
Physical Exam		X			
Nutritional Status (MNA)		X			
Permanent residence		X	X	X	X
Mean hospital stay			X		
Death			X	X	X
Frailty (Fried)		X	X		
Frailty(FRAIL)		X	X	X	X
EuroQolfive-dimensional (EQ-5D)		X	X	X	X
Caregiver burden		X	X	X	X
Relocation to other hospital services			X		
Adverse events (iatrogenic, falls, geriatric syndromes, etc.)		X	X		
Economics evaluation			X	X	X
Checklist of complementary test during the hospitalization			X		
Consultation to other specialist during hospitalization			X		

Coordination of care in different levels of care		X		
Readmission			X	X
Visits to the emergency room			X	X
Nosocomial infections		X		

* In case of surgical patients, who after 3 weeks since the first visit have passed and surgery hasn't been performed, evaluate the possibility of re-assessing inclusion criteria.

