3 OBJECTIVES

3.1 PRIMARY OBJECTIVE:

To assess the feasibility and effectiveness of programs designed to detect and manage frail older patients in high risk clinical settings, and to avoid functional impairment and other associated adverse outcomes. These high risk settings will be medical wards (cardiology, oncology or nephrology), major surgery wards and Emergency rooms.

3.2 SECONDARY OBJECTIVES:

- Determine the feasibility of implementing clinical and therapeutic approach to geriatric physician in elderly patients in high risk clinical settings
- Determine disability by evaluating basic and instrumental activities of daily living in frail elderly patients treated in high risk clinical settings.
- Establish functional status in frail elderly people seen in high risk clinical settings.
- Evaluate quality of life through an instrument validated in frail patients seen in high risk clinical settings.
- Establish mortality ratio in frail patients included in high risk clinical settings.
- Obtain the rate of re-hospitalization in frail patients seen in high risk clinical settings.
- Determine the average stay of hospitalization in frail elderly patients treated in high risk clinical settings.
- Obtain the rate readmission to emergency room and hospitalization in frail older patients treated in high risk settings.
- Determine the average stay of hospitalization in frail elderly patients treated in high risk clinical settings.
- Determine the rate of delirium in frail elderly patients in high risk settings.
- Obtain the rate of health-care associated infections in frail older patients seen in high risk settings.
- Determine the rate of polypharmacy in frail older patients seen in high risk settings.
- Establish the secondary institutionalization rate accordingly to decline the functional status in frail elderly patients in high risk settings.

- Determine the need for a caregiver as a result of decline the functional status in frail older people in high risk settings.
- Establish the caregiver burden in hospitalized frail patients on high risk settings.
- Establish the secondary institutionalization rate accordingly to decline the functional status in frail elderly patients in high risk settings.
- Determine the need for a caregiver as a result of decline the functional status in frail older people in high risk settings.
- Establish caregiver burden of frail elderly patients seen in high risk settings.

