4 OUTCOMES

4.1 PRIMARY OUTCOMES:

1. **Disability:** It was measured by the Barthel Index for basic Activities of Daily Living and the Lawton index for instrumental activities of daily living.
2. **Functional status and performance-based measures:** Functional status and performance-based measures: Is measured by Short Physical Performance Battery (SPPB), Physical Activity Scale for the Elderly (PASE SCALE).
3. **Quality of Life:** Quality of life was assessed by self-reported questionnaire EuroQL 5D 5L. It will be measured during admission to hospital and follow-up.
4. **Geriatrician Intervention:** The impact of their intervention is measured by quantifying in a register any additional tests requested and medical advice by other specialists.

4.2 SECONDARY OUTCOMES:

Prevalence of Delirium: The delirium cases are detected by Confusion Assessment Method (CAM) scale.

Cognitive Impairment: Will be measured by the Mini Mental State Examination (MMSE) in the initial assessment.

Depression: will be assessed using the Geriatric Depression Scale in the baseline assessment.

Health-care associated infections: Acquired during hospitalization start.

Geriatric Syndromes: The geriatric evaluation including the following aspects: clinical, functional, mental and social.

Comorbidity: Will measured at initial assessment thorough Charlson index

Nutritional Status: Will measured at initial assessment thorough the Mini Nutritional Assessment and body Mass index.

Polypharmacy: Defined as five or more prescription drugs.

Mortality rate: Number of deaths during follow-up. It is calculated using official report of the National Statistics Institute (INE).

Average stay hospitalization: Average length of stay of stay all discharges. We will obtain from Hospital Admissions service.

Hospitalization Rate in Emergency room: Number of hospital admissions over the total of patients admitted in the hospital.

Readmission rates: Number of readmissions during of follow-up period. I will get the data in Hospital Admissions Service.

Institutionalization: Number of patients referred to nursing home after discharge or at any time during follow-up. This information is obtained directly from patients or their relatives.

Requirement of caregiver: Number of patients who require a caregiver after hospital discharge.

Caregiver burden: Will be used Zarit Scale for assessing caregiver burden

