9 ASSESSMENTS DURING THE STUDY

9.1 BASELINE EVALUATION (visit 0= FIRST VISIT)

After the inclusion of a participant in the study, a comprehensive geriatric assessment will be done with the following parts:

Demographics and epidemiology: Date of birth, age, sex, race, caregiver, marital status, number of persons in the house, and, number of hospitalization in the last year, follow up by others specialist, level of education.

- Medical history

Personal Medical and Surgery History should be recorded in the electronic Case Report Form (eCRF).

- Medications:

In the CRF we register all the regularly medication use (previous hospitalization)

- Functional status

Evaluate functional status with the following scales: Barthel Index, Lawton Index, measures based in performance (SPPB-Short Physical Performance Battery) and PASE Scale, Annex 2.

- Cognitive and depression:

Evaluate the results with MMSE and Geriatric Depression Scale GDS, and delirium risk with CAM scale. See Index 2.

- Physical examination:

Vital signs and physical examination as usual by the clinical investigator.

- Geriatric Syndromes Assessment:

Immobility: Falls and imbalance.

Incontinence: urinary and fecal.

Sensory deprivation

Iatrogenic: Record the numbers of falls during the hospitalization and adverse effects

Pain: assess pain using the VAS Scale. Nutritional Status:

Performed screening for nutritional status using the scale MNA (Mini Nutritional Assessment), Index 2.

- Comorbidities:

Comorbidities will be quantified by Charlson Index, Index 2.

Quality of Life :

The evaluation for the quality of life using the EuroQol five-dimensional (EQ-5D), Index 2.

Caregiver :

- Assessment for the burden of the caregiver; Will be evaluated with The Modified Caregiver Strain Scale. Index 2.

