9.2 EVALUATION AT DISCHARGE FROM THE SPECIFIC CLINICAL SETTING

The following aspects will be assessed:

- Mortality
- Frailty assessment with L. P. Fried's scale and/or FRAIL scale. Functionality assessment with Barthel Index. Indicate the number of hospital stay in days .
- Describe if the patient change the Ward location/ medical /surgical in the hospital (UCI, Coronary unitetc) o)during the evolution in the hospital
- Quantification the number of test (Blood test, urine test, X- Ray, ecography, CT, etc and more specialized like: PET TAC, echocardiography, polisomnography, etc.)
- Quantification the number of consult with other specialist, social worker, palliative care. Etc.
- Usual treatment (Register all the medication at discharge
- Evaluate if the patient develop geriatric síndrome (page 22).
- Destination at dischargeia. (Nursing home, follow up by home care team, I HUG- GRT, day hospital, rehabilitation at home , specialist consultation, etc.)
- Evaluate the perception of the quality of life with the scale EuroQol five-dimensional (EQ-5D).
- Burden of the caregiver with the Economics questionnaire s.
- Economics evaluation Index 3

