Complementing the main cost-effectiveness analysis, we will develop several parallel cost effectiveness analysis to the extent that effective change. The results that we will use are: hospitalization rate and readmission, lenght of hospitalization and in the Emergency department, episodes of delirium and nosocomial infection, post-surgical complications as a whole and by surgical procedure, number of inappropriate drugs, adherence to treatment, permanent institutionalization rate, survival rate, preventable side effects due to under / over / mismanagement on caregiver burden.

Cost-utility analysis:

Cost-utility analysis (ACU) is an evolution of cost-effectiveness analysis, in which the interference effects are measured in a unit that synthesizes the lifespan and quality of life. The best and better known measure is the quality of life-adjusted per quality (QALY QALY or in its Anglo-Saxon sense). The QALYs are calculated by weighting the survival time (years of age) with quality adjustment thereof, called utility, which represents the preference values in relation to different health states (reference). For the purpose, the EQ-5D-5L instrument will be used. The incremental cost-utility relation answers the following expression:

$$\text{ACU}_{\text{incremental}} = (C_a - C_b) / (\text{AVAC}(a) - \text{AVAC}(b))$$

Statistical analysis:

A descriptive analysis of the main resources used in health care, social services and informal care will be performed.

This includes basic statistics such as means, medians, standard deviations, skewness, kurtosis, ranges, bivariate analysis using different cost elements and individual characteristics (sex, age,...) and health outcomes.

Because different distributions are expected from major cost components, we hope to develop different multivariate estimation methods. As we expect a non-normal distribution of the estimated costs, an alternative analysis would be the use of GLM models grouped by clusters, where depending on the distribution of the estimated costs (distribution Gamma, Poisson or Gaussian), will be used the most suitable method of empirical analysis. Another alternative, if the necessary information is obtained, could be an analysis using multilevel models of 2 or 3 grade (Recital country and center). The costs

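### Delirium is an effect outcome, but no CAM or other named delirium test is scheduled in both arms after the initial visit

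*Combined protocol and SAP*

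**What the plan says.** Delirium enters the plan as something the programme might change:

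- Section 3.2, secondary objectives: "Determine the rate of delirium in frail elderly patients in high risk settings".
- Section 4.2, secondary outcomes: "Prevalence of Delirium: The delirium cases are detected by Confusion Assessment Method (CAM) scale". No time point is given. In the same section, cognition, depression, comorbidity and nutrition are each tied to the initial or baseline assessment.
- Section 10 lists "episodes of delirium and nosocomial infection" among the results for cost-effectiveness analyses that run alongside the main one.

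The schedule is narrower:

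- Table 2 (section 9.5) has one row that contains the CAM, "Cognitive and depression (MMSE,GDS,CAM", with one mark, under Initial Visit.
- Section 9.1 lists the CAM within the baseline comprehensive geriatric assessment, as a measure of "delirium risk with CAM scale".
- Section 9.2 (discharge) has no CAM and does not mention delirium. Its nearest item is "Evaluate if the patient develop geriatric síndrome (page 22".
- Sections 9.3 and 9.4 are telephone contacts with no cognitive or delirium item.
- Table 2 also has an adverse-event row, marked at the Initial Visit and at Discharge, which includes geriatric syndromes but does not name delirium.
- Section 8.1 gives the control group a comprehensive geriatric assessment at admission and again at discharge. Section 8.2 gives the intervention group such an assessment without a time point. Table 2 marks this assessment at the Initial Visit only.

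**The concern.** The delirium that geriatric support could prevent arises during the hospital stay, after visit 0. A CAM at visit 0 comes before any plausible effect of the intervention, so comparing arms on it tests only chance imbalance at baseline. The gap is widest in surgical patients, because the footnote to Table 2 allows for surgery still not done three weeks after the first visit.

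At stake are one secondary objective, one secondary outcome and one complementary economic analysis. The loss cannot be made good later. The appended CAM form asks about acute change from baseline or fluctuation over the past 24 hours, so it cannot recover an episode from earlier in the stay, and the later contacts are by telephone.

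**Working it through.** The documents give no delirium rate, effect size or power, so there is no stated figure to reproduce. The check is of the schedule, followed by its statistical consequence.

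**1. Schedule, visit by visit**

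| Visit | Text | CAM row in Table 2 | Named delirium test in both arms |
|---|---|---|---|
| Initial visit | 9.1 lists the CAM | marked | yes |
| Discharge | 9.2: new geriatric syndromes, no CAM | blank | none |
| 3 months (phone) | 9.3: none | blank | none |
| 12 months (phone) | 9.4: none | blank | none |

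The count is 1 of 4 assessment visits, and 0 of the 3 after baseline. The blanks are unlikely to be an artefact of table extraction, because the text of 9.1 to 9.4 gives the same pattern and neighbouring rows (Barthel, frailty, EQ-5D) do carry discharge marks.

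**2. Section 8.1 read with 9.1**

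- 8.1: controls have a comprehensive geriatric assessment at discharge.
- 9.1: the CAM is part of that assessment at baseline.
- Together these may imply a discharge CAM in controls.
- 8.2 states no discharge assessment for the intervention group, and 9.2 and Table 2 show no discharge CAM for either group.

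So there is a possible later CAM in one arm only, in conflict with two other places. Testing one arm gives no valid between-arm comparison.

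**3. What a visit-0 comparison can show**

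Let p be the prevalence of a positive CAM at visit 0. Under 1:1 randomisation the expected difference is p − p = 0, whatever happens to patients afterwards. The rejection probability of a two-sided 5% test was computed for p = 0.05, 0.10 and 0.20, with 155 per arm (one setting, section 7.3) and 930 per arm (1860 / 2). It was 0.05 in every case, so power equals the significance level.

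**4. The economic analysis**

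Section 10 defines ICER = (Ca − Cb) / (Ba − Bb), with benefits measured as change from baseline. Delirium would be B, in the denominator. A change needs a second measurement, and none is scheduled in both arms, so the denominator has no valid estimate. The cost difference in the numerator is unaffected.

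**5. Illustration only: what measuring incident delirium could offer**

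Assume 10% to 30% of controls develop delirium and a risk ratio of 0.6 to 0.8. Neither range comes from the documents. If every incident case were detected:

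- 155 per arm: power 0.09 (10%, ratio 0.8) to 0.70 (30%, ratio 0.6).
- 930 per arm: power 0.33 to above 0.99 for the same two cases.
- With the 20% drop-out of section 7.3 (155 × 0.8 = 124 and 930 × 0.8 = 744 per arm): 0.08 to 0.60, and 0.27 to above 0.99.

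A single CAM at discharge would find fewer cases and so give less power. The overall comparison could still be informative; a comparison within one setting mostly would not be.

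**The case against.** The strongest reply is that the plan does record something after baseline. The geriatric-syndrome item in 9.2 points to a page that cannot be identified in the text available. Section 4.2 describes geriatric syndromes broadly enough to include the mental domain, and the adverse-event row is open-ended. Section 8.1 may bring a CAM at discharge for controls. A reader might infer that delirium after allocation is never tested or recorded at all. The documents do not support that, and this much of the reply stands.

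It does not rescue the comparison. Neither discharge item names delirium, a tool or a definition, and the syndromes listed in 9.1 do not include it: there the CAM sits with cognition and depression. Informal recording is also likely to differ by arm, because geriatricians are more involved in one of them. A CAM in controls alone has no counterpart.

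A second reply is that section 4.2 promises only prevalence, which one baseline CAM supplies. But section 7.4 names the prevalence rate as the first way in which intervention effects will be assessed, and section 10 needs episodes and change from baseline. Delirium is meant to carry an effect.

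A third reply is about weight. Delirium is one of many secondary outcomes, its economic use is complementary, and the sample size rests on disability. That is right, and it limits the importance of the point.

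**Conclusion.** The point holds in a limited form. No CAM or other named delirium test is scheduled in both arms after the initial visit. As scheduled, the delirium comparison is one of baseline status, with expected arm difference zero and rejection probability 0.05 whatever the true effect. The complementary delirium cost-effectiveness analysis has no valid effect estimate.

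This rests on two assumptions: that visit 0 precedes any plausible effect of the intervention (the documents do not say whether the baseline CAM comes before or after allocation), and that it is done alike in both arms.

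Two stronger inferences should be resisted. First, a reader might put a number on the missed cases: on an assumed incidence of 10% to 30%, 155 × 0.10 = 15.5 and 155 × 0.30 = 46.5 per group in each setting. The documents give no incidence, these figures ignore drop-out, and a CAM at discharge would not detect all such cases. Second, a reader might conclude that the trial's main findings are compromised. They are not, because no primary outcome depends on delirium. The change is worth making because it is cheap and the data cannot be recovered later.

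**What to change.** 1. Reconcile sections 4.2, 8.1, 8.2, 9.1, 9.2 and Table 2 on when delirium is assessed, with the same timing and method in both arms.
2. Add the CAM to section 9.2 and to the Discharge column of Table 2 for both arms.
3. Add one discharge eCRF item, with one definition for both arms, for any delirium episode recorded between visit 0 and discharge.
4. Define the CAM outcome as CAM-positive at discharge among patients CAM-negative at visit 0. Label it as point prevalence at discharge, and state how deaths before discharge are counted.
5. Use the record-based item for the delirium episodes in section 10, with a stated caution that recognition may differ between arms.
6. Keep the visit-0 CAM as a baseline variable.

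The cost is protocol and eCRF wording, plus one short scale at an existing two-arm visit, a few minutes per patient. The limitation is that episodes resolved before discharge are caught only by the record-based item, so neither measure is complete alone.

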8.2 INTERVENTION GROUP

Patients included in this Group will be treated by usual physician with the support of geriatrics team, who will do Comprehensive Geriatric Assessment to detect any problem in the elderly population in the clinical, functional, mental and social domains. The objective is to establish a strategy of intervention, treatment and follow-up to optimize resources and improve independency and quality of life..

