9.3 EVALUATION AT 3 MONTHS OF DISCHARGE

Re-evaluate the following aspects by phone :

- Mortality
- Functionality data (Barthel index , Lawton index , PASE Scale).
- Usual medication.
- Residency at the moment.
- Frailty with the FRAIL scale..
- Data of quality of life with the scale EuroQolfive-dimensional (EQ-5D)
- Number of hospitalization and ER, indicate the cause (diagnosis)
- Caregiver burden with the economic questionaries .
- Economics evaluation, Index 3

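### Dedicated collection of falls, adverse effects and geriatric syndromes ends at discharge, so in-hospital counts are confounded with length of stay and harms managed at home are missed

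*Combined protocol and SAP*

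**What the plan says.** - **Table 2 (section 9.5).** The row "Adverse events (iatrogenic, falls, geriatric syndromes, etc" is marked at the initial visit and at discharge. The 3- and 12-month columns are blank, whereas death, FRAIL, EQ-5D, caregiver burden and economics are marked at both calls.
- **Section 9.1.** Under geriatric syndromes: "Iatrogenic: Record the numbers of falls during the hospitalization and adverse effects".
- **Section 9.2.** Under the title "EVALUATION AT DISCHARGE FROM THE SPECIFIC CLINICAL SETTING", the list includes "Evaluate if the patient develop geriatric síndrome" and the number of days in hospital.
- **Sections 9.3 and 9.4.** The telephone lists cover mortality, Barthel, Lawton, PASE, "Usual medication", residence, FRAIL, EQ-5D, caregiver burden, economics, and hospitalisations and emergency visits with their cause. Neither list has an item for falls, adverse effects or new geriatric syndromes.
- **Section 4.2.** Geriatric syndromes are a secondary outcome with no time frame. So is length of stay: "Average stay hospitalization: Average length of stay of stay all discharges".
- **Section 7.4.** Events are to be analysed as a prevalence rate and, where possible, a duration. Survival models are foreseen only if dates of death and hospitalisation can be obtained. No bed-day denominator or fixed window is given for these harms.
- **Section 8.2.** On the intervention: "The objective is to establish a strategy of intervention, treatment and follow-up to optimize resources".

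**The concern.** Two problems follow from this schedule.

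First, the time during which a fall, adverse effect or new syndrome can be recorded is the patient's stay. A geriatric team working alongside the treating physician may shorten the stay, or lengthen it by finding more to treat. Either way the arms would be observed for different lengths of time, and a comparison of counts or prevalences per patient would mix the rate of harm with the length of observation.

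Second, the intervention sets a treatment and follow-up strategy whose effects can continue after the patient leaves. The calls ask which medicines the patient takes, but not whether they caused trouble or whether the patient has fallen. A fall or drug effect dealt with at home or in primary care is not recorded.

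At stake are a named secondary outcome (geriatric syndromes, under which section 9.1 lists falls), the safety description of the intervention, and some complementary economic analyses. The primary outcomes are not affected.

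**Working it through.** The plan states no figure on this point, so there is none to reproduce. The check compares the schedule with the text and then illustrates the size.

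**Step 1: is the blank in Table 2 only a missed mark?** No. Section 9.1 limits falls to the hospitalisation, 9.2 places the assessment of new syndromes at discharge, and neither 9.3 nor 9.4 lists these harms. Table and text agree.

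**Step 2: what is still seen after discharge?** Deaths; admissions and emergency visits with diagnosis; and, through the repeated Barthel Index, changes in bowel, bladder and mobility items. Section 9.1 lists incontinence and immobility among the geriatric syndromes, so these are partly visible. Falls and drug effects that do none of these things are not seen.

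**Step 3: how much of the observed time has dedicated collection?** The documents give no expected stay, so I assume L days, followed by 365 days (sections 9.4 and 9.5). Share = L / (L + 365).

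| Assumed L | Share |
|---|---|
| 5 | 5/370 = 1.4% |
| 10 | 10/375 = 2.7% |
| 20 | 20/385 = 5.2% |

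These are shares of time, not of harm. Risk is unlikely to be constant, and some later harm is captured as in step 2.

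**Step 4: what does a difference in stay do by itself?** Assume the same daily hazard h in both arms. Expected count per patient = h × L. Proportion with at least one event = 1 − exp(−h × L).

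| h (assumed) | Control stay | Intervention stay | Control proportion | Intervention proportion | Ratio |
|---|---|---|---|---|---|
| 0.005 | 10 | 8 | 0.0488 | 0.0392 | 0.80 |
| 0.010 | 10 | 8 | 0.0952 | 0.0769 | 0.81 |
| 0.005 | 10 | 7 | 0.0488 | 0.0344 | 0.71 |
| 0.010 | 10 | 7 | 0.0952 | 0.0676 | 0.71 |

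For counts at h = 0.005: 0.005 × 10 = 0.050 against 0.005 × 8 = 0.040, a ratio of 0.80. With the stays exchanged (8 days in control, 10 in intervention), the ratio of proportions is 0.0488/0.0392 = 1.24. The true hazard ratio is 1 throughout.

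**Step 5: which discharge closes the window?** The title of 9.2 refers to the specific clinical setting. In Table 1, four of the six sites recruit in the emergency room. Read literally, the window there may be far shorter than the hospital stay, and the bed-day denominator would have to match it.

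**The case against.** **The calls do see harm.** This stands in part. A reader might infer from Table 2 that no harm is recorded after discharge. The documents do not support that: both calls record deaths and the cause of each admission or emergency visit, and the Barthel items track continence and mobility. The gap is confined to harms that produce none of these.

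**The plan states no per-patient comparison of falls.** True for falls and adverse effects as such. Section 4 does not list them separately, and the instruction in 9.1 concerns collection only. But geriatric syndromes are a listed outcome, and 7.4 applies a prevalence rate to section 4 outcomes without an observation window. Hospital days are recorded, so the bed-day rate can be calculated, but nothing in the plan calls for it.

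**Fewer falls in a shorter admission is a real effect.** It is, on falls per admission. It misleads only when read as a lower daily risk or as fewer falls overall, which is how a reader of a safety table is likely to take it.

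**The direction is unknown.** This stands. It is tempting to conclude that the comparison is biased in favour of the intervention. That needs an assumption that the intervention shortens the stay, and the documents give neither an expected stay nor an expected change.

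**The economic evaluation is invalidated.** A reader might infer this, because section 10 uses "preventable side effects due to under / over / mismanagement on caregiver burden" and post-surgical complications as effects while Table 2 collects costs to month 12. The text does not go so far. The main effect is functional status, which is followed to the last call. The harm measures belong to complementary analyses with no stated cost horizon.

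**Conclusion.** The point holds in a limited form. Dedicated collection of these harms stops at discharge, and afterwards only those leading to death, hospital contact or a Barthel change are seen. In hospital, a count or prevalence per patient cannot be separated from length of stay, itself a secondary outcome.

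That the two are confounded follows from the schedule. The sign and size do not: the ratios of 0.71 to 0.81, and 1.24 in the other direction, rest on assumed stays and a constant, equal daily hazard. Secondary, safety and complementary economic results are affected. The change is worth making because it is inexpensive.

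**What to change.** 1. **Reconcile the follow-up times first.** Section 7.2 gives the third and sixth month after discharge; 9.4, 9.5 and Table 2 give 12 months. State also whether the in-hospital window closes at discharge from the setting or from the hospital.
2. **In-hospital harms.** Report falls, adverse effects and new geriatric syndromes per bed-day as well as per patient, with a denominator that matches the window. The length of stay is already recorded. A bed-day rate removes the confounding fully only if the hazard is roughly constant over the stay, so it does not replace item 3.
3. **After discharge.** Mark the Table 2 adverse-event row at both calls. Ask, with the same script in both arms, for the number of falls (injurious or not), adverse drug effects needing medical contact and, for surgical patients, post-surgical complications, each with an approximate date.
4. **Analysis.** Compare events over fixed windows from randomisation that every patient's schedule covers, or as person-time rates over stay plus follow-up, with person-time ending at death. The dates are essential: the calls are timed from discharge, so a count since the last contact covers stay plus 3 months, and that total still varies with stay.

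**Cost.** A few questions in calls already made and one extra denominator; no new visit. The limits should be stated. On the 12-month schedule, recall spans about 9 months (12 − 3) and will be weak. Patients know whether they had geriatric support, so reporting may differ between arms even with the same script. Drug effects that led to no medical contact would still be missed.
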